5.10 Investigational Product Retention at Study Site

All investigational drug products supplied to the Investigator must be accounted for in this study. Study medication must be kept in a secured location, and all medication should be returned to the study site and retained until the study close-out.

6 STUDY PROCEDURES

6.1 Informed Consent

Prior to entry into the study or initiation of any study-related procedures, the subject must read, sign, and date the current IRB-approved version of the informed consent form. In the case of a minor subject, fully informed consent must be obtained from the parent/legal guardian in accordance with local legal requirements and IRB requirements. Where appropriate, minor study subjects should assent to enroll in this study (with age of assent to be determined by the IRB and be consistent with local legal requirements). The original informed consent form is to be retained by the study site, and a copy is to be given to the subject. Section 10.3 provides details of the administration of subject information and consent.

6.2 Medical History

A complete medical history, including previous or current diseases or illness, will be obtained at the baseline visit. A complete surgical history should also be documented.

The ocular history will include any previously diagnosed ophthalmic abnormalities and ocular surgeries (including laser procedures).

A urine pregnancy test will be administered at entry if the Investigator determines this is necessary.

6.3 Dispensing Study Drug

A supply of study drug or vehicle, as allocated, will be provided to each subject who meets inclusion/exclusion criteria at baseline. Subjects will be instructed to administer 1 drop per eye of study medication BID. The first dose will be administered by the subject under study personnel supervision; subjects will self-administer treatment for the remainder of the trial. To facilitate drug accountability and compliance, subjects will be instructed to return used, emptied containers at each subsequent study visit. Subjects will also be instructed to return all remaining containers, used or unused.

Artificial tears (Refresh Plus[®]) will be dispensed to subjects for use during the treatment period. **Subjects will be instructed to use the artificial tears only as needed up to 8 times per day. Subjects also will be instructed not to use the artificial tears within 30 minutes of instilling the study drug.** All other artificial tear products, including any topical ophthalmic medications other than the assigned study medication, must be discontinued from screening/baseline through Day 90. Subjects will be instructed to return used, emptied containers at each subsequent study visit. Subjects will also be instructed to return all remaining containers, used or unused, on Day 90

6.4 Efficacy Assessments

Efficacy will be assessed using objective (lissamine green staining, corneal fluorescein staining, and Schirmer test) and subjective (symptom frequency rating and symptom intensity rating) measures in both eyes.

6.4.1 Objective Efficacy Parameters

6.4.1.1 Lissamine Green Staining of the Cornea and Conjunctiva

Corneal and conjunctival staining will be performed in both eyes using 1 drop of 1% lissamine green solution, with results observed in low to moderate intensity white light of the slit lamp between 1 and 4 minutes following instillation. The areas evaluated will be the cornea and the nasal and temporal conjunctiva. Each area will be graded as follows:

- 0 = 0%
- 1 = 1%–15%
- 2 = 16%–30%
- 3 = 31%–45%
- 4 = >45%

The Investigator will record a score for each area (cornea, nasal conjunctiva, and temporal conjunctiva) of each eye. The scores for each eye will be summed. Lissamine green staining will be performed at all study visits.

6.4.1.2 Corneal Fluorescein Staining

Fluorescein staining of the corneal epithelium will be performed in both eyes at all study visits. Dye will be placed in the eye using blotting paper impregnated with fluorescein dye moistened with a full single drop (must be at least 10 μ L) of balanced salt solution (BSS). The subject will be asked to blink several times in order to disperse the dye uniformly. The cornea will be examined 3 minutes after instillation using the cobalt blue filter of the slit lamp and a Wratten #12 yellow filter to view the surface of the eye and identify abnormalities where staining appears.

Corneal Stain Intensity

Regarding corneal stain intensity scores, 5 specific areas of the cornea will be identified: area 1=central (defined as the central 5 mm of the cornea), area 2=temporal, area 3=inferior, area 4=nasal, and area 5=superior. Fluorescein staining of each corneal area will be graded on a 0-3 scale:

- 0=No staining
- 1=Mild staining
- 2=Moderate staining
- 3=Severe staining

To evaluate for central corneal clearing, the Investigator will record the corneal stain intensity score for area 1 (central).

The Investigator will also record scores for areas 2, 3, 4, and 5. The scores for areas **1-4 only (central, temporal, inferior, and nasal)** will be summed to tabulate a total score per eye for corneal stain intensity.

Corneal Stain Summed Score

To achieve a summed score in corneal fluorescein staining, each of 3 characteristics (ie, type, extent/surface area, depth) will be graded on a 0-4 scale:

5. Type

- 0 = No staining
- 1 = 2-5 areas of punctate staining
- 2 = >5 up to 15 areas of punctate staining or 1 area of coalesced staining
- 3 = >15 areas of punctate staining or 2 or more areas of coalesced staining or any area of epithelial or stromal diffusion of fluorescein
- 4 = >15 areas of punctate staining and 2 or more areas of coalesced staining and a frank corneal epithelial defect

6. Extent/Surface Area

- 0 = 0%
- 1 = 1%–15%
- 2 = 16%–30%
- 3 = 31%–45%
- 4 = > 45%

7. Depth

- 0 = No staining
- 1 = Superficial epithelium
- 2 = Deep epithelium, delayed stromal glow
- 3 = Immediate localized stromal glow
- 4 = Immediate diffuse stromal glow

The Investigator will record the score for each characteristic (type, extent/surface area, and depth). These scores will be used to tabulate a summed score per eye for corneal fluorescein staining.

6.4.1.3 Schirmer Test

The Schirmer test will be performed in both eyes with anesthesia for all study visits. The subject should be sitting comfortably in a room without extremely bright lighting. Two drops of topical anesthetic will be instilled into each eye 2 minutes before insertion of the Schirmer strips. The eye should be lightly blotted with tissues to remove excess anesthetic or tears. The

filter paper strips will be placed at the junction of the middle and lateral 1/3 of the lower eyelid, avoiding contact with the cornea. Strips should be placed in both eyes at the same time and timed for 5 minutes. The subject may sit with their eyes gently closed during this period and should avoid excessive blinking during the test. Strips will be removed after 5 minutes and the amount of wetting is recorded in millimeters (mm). The subject should be reminded not to rub his/her eyes for at least 30 minutes after the completion of the test.

6.4.2 Subjective Efficacy Parameters

6.4.2.1 Symptom Frequency

Symptom frequency will be assessed at all study visits, according to the following rating scale, for 7 symptoms: burning/stinging, itching, grittiness/scratchiness/foreign body sensation, dryness, stickiness, redness of the eye, and tired eye sensation:

- 0 = Never
- 1 = Sometimes
- 2 = Often
- 3 = Constantly

The subject will rate each of the 7 dry eye symptoms using the scale and each symptom score will be recorded by the Investigator. These scores will be summed to arrive at a total symptom frequency score.

6.4.2.2 Symptom Intensity

The Visual Analogue Scale (VAS) will be used at all study visits to assess the presence and severity of dry eye symptoms: burning/stinging, itching, grittiness/scratchiness/foreign body sensation, dryness, stickiness, redness of the eye, and tired eye sensation on a 0-100 mm scale (0 = absent and 100 = severe). The subject marks the point on the scale that best depicts each symptom, and the distance between the 0 point and the subject's mark is measured in mm and recorded by study personnel.

6.5 Safety Assessments

Safety will be assessed using objective (BCVA, slit lamp examination, ophthalmoscopy, and IOP measurement) and subjective (subject comfort and tolerability) measures in both eyes, unless otherwise specified.

6.5.1 Best-Corrected Visual Acuity

BCVA measurement will be performed at all study visits with the Snellen eye chart (using the subject's current corrective lens prescription) at a distance of 20 feet (6 meters).

6.5.2 Slit Lamp Examination

A routine slit lamp examination will be performed at all study visits to evaluate the anterior segment of the eye, including lids, cornea, sclera, conjunctiva, lid margins, lens, and capsule. Abnormalities will be documented.

6.5.3 Ophthalmoscopy

Direct ophthalmoscopy will be performed at baseline and at Day 90.

6.5.4 Intraocular Pressure

All IOP measurements will be performed utilizing Goldmann applanation tonometry using standard of care. To avoid changes due to the diurnal rhythm, the IOP in a given subject should be recorded at approximately the same time of day throughout the study. IOP measurement will be conducted at baseline, and Days 28 and 90.

6.5.5 Subject Comfort and Tolerability

An evaluation of subject comfort following the first (Day 0) and last (Day 90) instillations of the study medication will be performed. Subjects will rate their experience of burning, stinging, and blurring of vision following instillation of study drug using the following scale:

- 0 = Absent
- 1 = Mild
- 2 = Moderate
- 3 = Severe

6.6 Adverse Events Assessments

An AE is any untoward medical occurrence in a subject administered a medicinal product and which does not necessarily have to have a causal relationship with this treatment. An AE can therefore be any unfavorable and unintended sign (eg, an abnormal laboratory finding), symptom, or disease temporally associated with the use of a medicinal product, whether or not considered related to this medicinal product.

6.6.1 Performing Adverse Events Assessments

AEs will be assessed by the Investigator at each study visit, once subjects receive the first dose of study drug. The first dose of study medication will be administered by the subject under study site personnel supervision and the **subjects will be observed for any AEs over the ensuing 30 minutes**. Any and all abnormalities seen by physical, ocular, and ophthalmic examination will be noted.

To further elicit AEs, simple questions with minimal connotations will be used as the initial questions at all evaluation points during the trial.

For example:

- How do your eyes feel?
- Have you had any health problems since your last assessment?

The AE probe will be conducted by the same study personnel for each visit for an individual subject, if at all possible.

All AEs, regardless of severity and whether or not they are ascribed to the study treatment, will be recorded using standard medical terminology. The onset, duration, severity, action taken, relationship to treatment, and outcome of all AEs will be documented in the eCRF. The Investigator must assess (and record in the eCRF) the degree to which the event was related to the study medication. Subjects with an AE should be carefully followed to determine outcome until resolution or 30 days after the last study visit, whichever comes first. If no AE has occurred, this should be noted in the appropriate place on the AE section of the eCRF.

6.6.2 Timing

Any AE that begins on or after baseline (Day 0) following the initial dose of study medication until the end of the treatment period (Day 90) is to be recorded in the appropriate section of the eCRF. Subjects with an AE should be carefully followed to determine outcome until resolution or 30 days after the last study visit, whichever comes first.

6.6.3 Severity

The Investigator will use the following definitions to code the intensity of the event:

- **Mild** Usually transient, requiring no special treatment, and does not interfere with the subject's daily activities
- **Moderate** Traditionally introduces a low level of inconvenience or concern to the subject and may interfere with daily activities, but are usually relieved by simple therapeutic measures
- **Severe** Causes an interruption of the subject's usual daily activity and traditionally requires systemic drug therapy or other treatment

There is a distinction between the severity and the seriousness of an AE. Severe is a measurement of intensity; thus, a severe reaction is not necessarily an SAE. For example, a headache may be severe in intensity, but would not be serious unless it met one of the criteria for SAEs listed in Section 6.6.7.1.

6.6.4 Relationship

The relationship or association of the study medication to an AE, as causing or contributing to the AE, will be characterized as defined below:

- **Not related** Evidence indicates no plausible direct relationship to the study medication
- **Unlikely related** Suggests other conditions are reasonably likely to account for the event including concurrent illness, progression, or expression of the disease state, or reaction to concurrent medication
- **Possibly related** Suggests that the association of the event with the study medication is unknown; however, the AE is not reasonably supported by other conditions
- **Related** Follows anticipated response to study medication and is confirmed by discontinuing and/or rechallenge

Procedures such as surgery should not be recorded as AEs. However, the medical condition for which the procedure was performed should be reported if it meets the definition of AE as described previously.

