6.6.5 Expectedness

In a previous clinical trial where CSA concentrations ranged from 0.1% to 0.4% in the treatment of moderate-to-severe dry eye, AEs were uncommon and no significant AEs were reported (Stevenson, 2000).

In more recent studies by Sirion Therapeutics comparing CSA 0.1% to vehicle in treating moderate-to-severe dry eye, the AE's reported most frequently among both the CSA-treated and vehicle-treated subjects were as follows: eye irritation, conjunctival hyperaemia, ocular hyperaemia, dry eye, and foreign body sensation in eyes (Data on File, 2008).

Unexpected AEs are defined as any AE, the specificity or severity of which is not consistent with the current Investigator's Brochure.

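### The causality grades in section 6.6.4 leave nothing above 'Unlikely related' for an unconfirmed event that both the drops and dry eye could explain, and bar unanticipated reactions from 'Related'

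*Protocol*

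**What the plan says.** Section 6.6.4 asks the investigator to grade the study medication as a cause of, or contributor to, each adverse event. Apart from 'Not related' (no plausible direct relationship), the grades are, from the top:

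- The highest grade, 'Related', is worded: "Follows anticipated response to study medication and is confirmed by discontinuing and/or rechallenge". Both conditions must be met.
- One step down, the text for 'Possibly related' reads: "Suggests that the association of the event with the study medication is unknown; however, the AE is not reasonably supported by other conditions".
- Below that, the text for 'Unlikely related' includes: "Suggests other conditions are reasonably likely to account for the event including concurrent illness, progression, or expression of the disease state". Effects of other medicines count as such a condition too.

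Section 6.6.5 lists the most frequent events in the sponsor's recent CSA 0.1% studies, in CSA-treated and vehicle-treated subjects alike: "eye irritation, conjunctival hyperaemia, ocular hyperaemia, dry eye, and foreign body sensation in eyes". It gives no rates. Expectedness is defined there separately: "Unexpected AEs are defined as any AE, the specificity or severity of which is not consistent with the current Investigator's Brochure".

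Section 6.4.2.1 scores these as symptoms of dry eye: "burning/stinging, itching, grittiness/scratchiness/foreign body sensation, dryness, stickiness, redness of the eye, and tired eye sensation".

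**The concern.** Every subject has dry eye, so the disease is a standing alternative explanation for most ocular complaints. A causality scale for such a trial needs a grade for an event that the drug may have caused but the disease could also explain. Section 6.6.4 has none, unless the event meets both conditions for 'Related'. It also brings expectedness into causality by requiring that a 'Related' event be anticipated.

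Safety is part of the primary objective (section 2.1), and section 1.5 says the study is designed to compare safety points between 0.1% and 0.2%. Section 6.6.1 requires a relatedness grade for every event. If the grades lean downward for the commonest events, any summary of attributed events will too.

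**Working it through.** The protocol states no drug-related event rate, so there is no figure to reproduce. The check is of the definitions, followed by an illustration on assumed rates.

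**Step 1: an event with two plausible causes.** Take a subject with eye irritation that the drops and dry eye could each reasonably explain, who keeps dosing.

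- 'Related' fails: there is no confirmation by discontinuing or rechallenge.
- 'Possibly related' fails: another condition reasonably supports the event.
- 'Unlikely related' fits: it names expression of the disease state.

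No grade above 'Unlikely related' remains. Yet the lead sentence of 6.6.4 includes contribution as well as causation, and a contributing cause normally exists beside another cause.

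**Step 2: an unanticipated reaction with positive dechallenge.** 'Related' joins its two conditions with 'and', so this reaction fails. With no competing explanation, the best grade left is 'Possibly related', whose text calls the association unknown although dechallenge has just supported it.

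**Step 3: which events are touched.** Set the section 6.6.5 terms against the section 6.4.2.1 symptoms:

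| Frequent adverse event (6.6.5) | Symptom scored as dry eye (6.4.2.1) |
|---|---|
| Eye irritation | Burning/stinging, grittiness |
| Conjunctival hyperaemia | Redness |
| Ocular hyperaemia | Redness |
| Dry eye | Dryness |
| Foreign body sensation | Foreign body sensation |

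All 5 of 5 overlap. A product effect is also plausible on the protocol's own evidence. Section 1.4.1 reports slight conjunctival hyperemia in 1 to 2 healthy volunteers at various visits on the earlier CSA 0.1% product. Section 1.3 reports conjunctival redness in dogs at 0.1% to 0.4%, with low prevalence on placebo. Section 1.2 says the vehicle contains a preservative and surfactants.

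**Step 4: the confirmation clause alone.** Consider events that no other condition supports. Those lacking confirmation move from 'Related' to 'Possibly related'. With an assumed true related rate of 20%:

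- Both grades pooled: 20% whatever the share lacking confirmation.
- 'Related' only: 20% × (1 − 0.5) = 10% if half lack it, and 20% × (1 − 1) = 0% if all do.

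So this clause lowers a rate only if the two grades are not pooled. The pages at hand do not say.

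**Step 5: illustration of the gap.** Let s be the share of truly drug-caused events graded 'Unlikely related', the same in each arm. The reported rate is the true rate × (1 − s). With 65 per arm and two-sided 0.05, power = Φ[(Δ − 1.96·SE0)/SE1], where Δ is the difference in reported rates, SE0 = √[2p̄(1 − p̄)/65] and SE1 = √{[p1(1 − p1) + p2(1 − p2)]/65}. For 5% against 20% and s = 0: SE0 = 0.0580, SE1 = 0.0565, and (0.15 − 1.96 × 0.0580)/0.0565 = 0.64, so power is 0.740.

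| s | True 5% / 20%: reported | Difference (points) | Power | True 10% / 25%: reported | Power |
|---|---|---|---|---|---|
| 0 | 5% / 20% | 15 | 0.740 | 10% / 25% | 0.617 |
| 0.25 | 3.75% / 15% | 11.25 | 0.597 | 7.5% / 18.75% | 0.475 |
| 0.50 | 2.5% / 10% | 7.5 | 0.422 | 5% / 12.5% | 0.326 |
| 0.75 | 1.25% / 5% | 3.75 | 0.231 | 2.5% / 6.25% | 0.179 |

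The rates and s are assumptions. The ratio between arms is unchanged (4 in the first set, 2.5 in the second), while the absolute difference and the power shrink.

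**The case against.** The strongest reply is that the grades rest on judgement, and that the main safety comparisons do not use them.

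- **Judgement.** Whether another condition is reasonably likely to account for an event is for the investigator to decide. Symptoms are scored at baseline and every visit, and the first dose is supervised with 30 minutes of observation (section 6.6.1). Irritation that starts at instillation and differs from baseline can be judged not supported by the disease, and so 'Possibly related'. This stands: the scale steers grades downward but does not fix them. It does not help where both causes remain reasonable, as may happen with redness or foreign body sensation between visits.
- **Disease attribution may be right.** The frequent events occurred in both CSA and vehicle subjects, and the protocol does not show that they were drug-caused. This stands, and it is one reason why the size is unknown.
- **Other safety data are intact.** Section 6.6.1 says: "All AEs, regardless of severity and whether or not they are ascribed to the study treatment, will be recorded using standard medical terminology". All-cause incidence by arm is therefore available in a randomised, masked comparison. Section 6.5.5 adds a rating with no causality grade: "Subjects will rate their experience of burning, stinging, and blurring of vision following instillation of study drug using the following scale". This stands too, although that rating is taken only on Days 0 and 90 and omits hyperaemia and foreign body sensation.

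A reader might infer that related-event counts fall to zero in all arms and that a dose difference is hidden. The documents do not support that. A zero count needs every event to be drug-caused, every subject to keep dosing and every investigator to take the strictest reading. A dose difference would still be open to view in all-cause incidence.

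A reader might also infer that an unanticipated serious event would be kept from the sponsor. Section 6.6.7.2 has serious events entered within 24 hours of notification and the review board told regardless of cause. Only the causality grade suffers.

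**Conclusion.** The point holds as a defect in the definitions. Section 6.6.4 has no grade above 'Unlikely related' for an unconfirmed event that drug and disease could both reasonably explain, and it denies 'Related' to an unanticipated reaction whatever the confirmation. It is at odds with its own lead sentence and covers all five frequent event terms in section 6.6.5.

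The likely direction is understatement of causally attributed ocular events, vehicle arm included. The size is unknown. The power figures above only show how the loss would grow under assumed rates and an equal diverted share in each arm, which masking (section 5.5) makes reasonable. All-cause adverse events, comfort ratings and serious-event reporting do not depend on this scale. Which grades count as treatment-related is not stated in the pages at hand and is not part of this point.

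**What to change.** Redefine three grades in section 6.6.4 so that they neither leave a gap nor overlap, and keep 'Not related' as it is:

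- **Unlikely related:** another cause is clearly more likely than the study medication.
- **Possibly related:** the time relationship to dosing is reasonable and a drug effect is plausible, although the disease or another condition could equally explain the event.
- **Related:** the time relationship is reasonable and the study medication is more likely than any other cause. Dechallenge or rechallenge supports this grade but is not required. The response need not be anticipated, because expectedness is judged separately in section 6.6.5.

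The completion guide should add that an event for which another cause is somewhat, but not clearly, more likely belongs in 'Possibly related'.

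The cost is protocol wording and the eCRF guide, settled before grading starts. Treatment, visits and sample size do not change. The small downside is that more events will be graded possibly related in all arms, including vehicle.
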